Between the extension study entry visit (week 25) and the EOS (week 49), newly enrolled patients will only visit the site once for the week 37 visit. In between the visits, the patients will be contacted monthly by phone by the site personnel to enquire on the patient's health status and to check compliance with the  diaries.

For a complete and detailed list of assessments, please refer to [Section 6](#) and [Table 6-1](#).

End of study (EOS)/Week 49

This is the last planned visit in the study. It will take place at week 49 or earlier in case of premature study discontinuation.

Following the EOS visit, the patient will be followed by his/her treating physician according to the local standard of care and the patient's situation.

For a complete and detailed list of assessments, please refer to Section 6 [Table 6-1](#).

[figure not shown]
[figure not shown]

Figure 3-2 Study design for patients enrolled prior to protocol amendment #1

Management of patients enrolled prior to the protocol amendment #1

Patients enrolled prior to the study amendment #1 will continue to be dosed every 4 weeks until week 49 (EOT) and will then have a 4 weeks follow-up period until week 53 (EOS).

These patients will also continue the exercise program described above.

Please refer to [Section 6](#) and the specific [Table 6-2](#) for a complete and detailed list of assessments for these patients.

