5.5.4 Instructions for prescribing and taking study treatment

Section only applicable to patients enrolled prior to the protocol amendment#1.

[REDACTED]
[REDACTED] End of infusion

will be considered as the time of the end of the line flush. All times stated within this protocol are from the start of study drug administration (unless otherwise stated).

Infusions will occur every 4 weeks, after all pre-dose assessments have been performed. Six doses will be administered during the course of the study (see [Section 3.1](#)).

Only the materials (infusion bag, administration set and filter) specified in the pharmacy manual should be used for administration of the study medication.

All dosages prescribed and dispensed to the patient during the study must be recorded on the Dosage Administration Record electronic case report form (eCRF) page.

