5.5.10 Discontinuation of study treatment or from study

For patients enrolled prior to the protocol amendment#1.

Individual subject discontinuation

The investigator should discontinue study treatment for a given patient if, on balance, he/she believes that continuation would be detrimental to the subject's well-being.

Investigational treatment must be discontinued under the following circumstances:

- Use of prohibited treatment as per [Table 5-1](#).
- Any other protocol deviation that results in a significant risk to the patient's safety
- Breaking of the blind (inadvertently or for emergency reasons)
- Severe hypersensitivity reaction occurs

- Liver event definition met as per [Appendix 1](#)
- Total of two (2) doses were missed in the entire study
- Death
- Withdrawal of consent
- Sponsor decision to terminate (part of) the study

Investigational treatment may be discontinued under the following circumstances:

- Emergence of one or more adverse events that in the judgment of the investigator, taking into account the patient's overall status, prevent the patient from safely continuing in the study
- Any laboratory abnormalities that in the judgment of the investigator, taking into consideration the patient's overall status, prevents the patient from safely continuing in the study

Patients who discontinue study treatment should NOT be considered withdrawn from the study UNLESS they withdraw their consent (see [Section 5.5.11](#)). They should return as close to 28 days since the last dose received and complete the EOT visit and enter the Post-treatment follow up. The EOS visit should be scheduled 4 weeks after EOT. If they fail to return for these visits for unknown reasons, every effort should be made to contact them as specified in [Section 5.5.12](#).

At a minimum, patients will be contacted for safety evaluations during the 30 days following the last study visit, including a final contact at the 30-day point. Documentation of attempts to contact the patient should be recorded in the source documentation. Investigators or site personnel must contact the IRT to register the patient's discontinuation from treatment.

For patients enrolled after the protocol amendment#1.

Patients have to be discontinued from the study if they receive any of the prohibited medication listed in Section 5.5.9.

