5.5.15 Early study termination

The study can be terminated at any time for any reason by Novartis. Should this be necessary, the subject should be seen as soon as possible and treated as a prematurely discontinued subject. The investigator may be informed of additional procedures to be followed in order to ensure that adequate consideration is given to the protection of the subject's interests. The investigator will be responsible for informing IRBs/IECs of the early termination of the trial.

6 Visit schedule and assessments

For patients enrolled after the protocol amendment #1, the full assessment schedule is presented in [Table 6-1](#) below. Patients enrolled prior to the protocol amendment #1 will be followed according to the visit scheduled presented in [Table 6-2](#).

In order to allow sufficient reflection time for the informed consent process, the extension study may be presented and discussed early enough in the core study in order to allow the ICF signature process to be done at the Week 25/core EOT visit. The ICF must not be signed before the core EOT visit to avoid complications in the safety reporting requirements.

Patients following [Table 6-1](#) should be seen for all visits on the designated day within a recommended 'visit window' of +/- 14 days. Day 1 must be the same day as the EOT visit of the core (i.e. the visit date is the date of the EOT visit of the core).

Patients should arrive to the visit fasted when blood samples for laboratory assessments will be taken at that visit.

Assessments for a particular visit may be split over several days. These may not be consecutive days but should respect the visit window period.

Below are some recommendations for organizing and performing the study assessments at visits with blood sampling.

- Assessments should be performed sequentially in the morning as follows: ECG collection, vital signs, blood sampling.
- After blood sampling, patients should be offered breakfast.

For patients enrolled prior to the protocol amendment #1, the visits window to be applied is +/- 3 days. When scheduling the assessments of a visit, the same principle as stated above should apply. In addition, study treatment administration should be the last procedure.

[figure not shown]

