Patients who discontinue the study should **NOT** be considered withdrawn from the study UNLESS they withdraw their consent (see [Section 5.5.11](#)). They should return and complete the EOS visit. If they fail to return for these visits for unknown reasons, every effort should be made to contact them as specified in [Section 5.5.12](#).

Patients enrolled prior to the protocol amendment #1, who prematurely discontinue study treatment, should return as close to 28 days following the last dose received and complete the EOT visit. Their EOS visit should be scheduled 4 weeks after their EOT.

At a minimum, patients will be contacted for reporting and follow-up of serious adverse events during the 30 days following the last study visit, including a final contact at the 30-day point. Documentation of attempts to contact the patient should be recorded in the source documentation.

Table 6-1 Assessment schedule for patients enrolled after the protocol amendment #1

Epoch	Screening epoch	Post-treatment follow-up epoch						
Timepoint	1	1	2	3	4	5	6	7
Site Visit	1(EOT)	1 (EOT)			2			3 (EOS) ⁵
Phone contact			X	X		X	X	
Month	7	7	8	9	10	11	12	13
Week	25	25	29	33	37	41	45	49
Day	1	1	29	57	85	113	141	169
Obtain Informed consent	x							
Inclusion/Exclusion criteria	x							
Relevant medical history		x ²						
Demography	x							
Physical examination		*			s			s
Body weight		*1			x			x
Body height		*1						
Blood pressure/pulse rate (sitting)		*1			x			x
Electrocardiogram		*1			x			x
Laboratory samples (hematology, biochemistry, vitamin D)		*			x			x
Vitamin D3 supplementation		Equivalent to daily administration of 800 IU to 4000 IU						
Supervised exercise		*1			x			
Home based exercise		2-3 times per week						
6 minute walk test		*1			x			x
Short physical performance		*1			x			x

[figure not shown]

Epoch	Screening epoch	Post-treatment follow-up epoch						
battery								
Exercise diary		Daily by the patient to report level of home based exercise						
DXA		*						x
Diet assessment/ nutritional status		*1			x			x
AE ³ /SAE ⁴		x ²	Any time as per AE/SAE reporting requirement					
Concomitant therapies		x ²	Any time as per Concomitant therapies reporting requirement					
Comments	Any time as per investigator judgement							
Epoch disposition	x							x

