### 3.4.2 Statistical model, hypothesis and method of analysis

For Population I, a 95% confidence interval for the difference in the primary endpoint between each continued BYM338 dose arm vs. corresponding placebo switched from the same BYM dose will be calculated at Week 49. The CI of the difference will be calculated using a t-test comparing the values at Week 49 between BYM338 dose arms vs. corresponding placebo. Summary statistics will also be presented by treatment arm.

For Population II, the summary statistics will be presented by treatment assigned in the core study.

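### Population I patients who stop infusions early stay in the study but have no scheduled SPPB in the Week 49 window, so they drop out of the observed-data primary contrast

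*Protocol*

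**What the plan says.** The point concerns only patients enrolled before protocol amendment 1 (Population I), who are still dosed in the extension.

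- **Status after stopping infusions.** Protocol 5.5.10: "Patients who discontinue study treatment should NOT be considered withdrawn from the study UNLESS they withdraw their consent".
- **Visits after stopping.** The same paragraph continues: "They should return as close to 28 days since the last dose received and complete the EOT visit and enter the Post-treatment follow up". It then adds: "The EOS visit should be scheduled 4 weeks after EOT". Protocol Section 6 repeats the rule ("Their EOS visit should be scheduled 4 weeks after their EOT"), as does footnote 4 of Table 6-2. Nothing in the protocol asks these patients to come back at calendar Week 49.
- **Full schedule.** Protocol 5.5.4: "Six doses will be administered during the course of the study". Table 6-2 puts the doses at Weeks 25, 29, 33, 37, 41 and 45, EOT at Week 49 (Day 169) and EOS at Week 53 (Day 197). On the timing of visits, Section 6 says that "the visits window to be applied is +/- 3 days".
- **Primary analysis.** The endpoint is SPPB at Week 49 (Protocol 9.4.1) on the FAS, which is everyone enrolled (9.1, 9.4.2). Data are analysed as observed, without imputation apart from a balance-item rule (Protocol 9.4.3, SAP 3.4.3). For Population I, SAP 3.4.2 says: "The CI of the difference will be calculated using a t-test comparing the values at Week 49 between BYM338 dose arms vs. corresponding placebo".
- **Visit assignment.** SAP 5.5.1 assigns values by study day. Week 49 is Days 156 to 183.

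**The concern.** These provisions do not fit together. A patient who stops infusions remains in the study and in the FAS, but the visit rule ends assessments well before the primary time point in most cases. The absence is then built in by schedule, and the analysis simply omits the patient.

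Continued versus switched, within the same core dose, is the only comparison of different regimens randomised within this extension (Protocol 5.2). Protocol 3.2 keeps these patients on their original dosing so as to learn as much as possible about those regimens. The arms are very small, so each missing Week 49 value costs precision. If stopping is related to treatment and to later function, the contrast may also be biased. Only the continued arms still receive active drug. Some stop rules in 5.5.10 (liver event, severe hypersensitivity, adverse event or laboratory judgement) could be drug-related, and Protocol 3.6 reports transient AST and ALT rises on bimagrumab.

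**Working it through.** **1. Reproduce the planned schedule.** Doses fall on Days 1, 29, 57, 85, 113 and 141. Last dose 141 + 28 = 169 (EOT); 169 + 28 = 197 (EOS). Both match Table 6-2.

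**2. Apply the early-stop rule.** EOT = last dose + 28; EOS = last dose + 56. Each visit is mapped to the SAP 5.5.1 windows.

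| Last dose | EOT day (SAP week) | EOS day (SAP week) | Visit in Days 156 to 183? |
|---|---|---|---|
| Week 25, Day 1 | 29 (29) | 57 (33) | none |
| Week 29, Day 29 | 57 (33) | 85 (37) | none |
| Week 33, Day 57 | 85 (37) | 113 (41) | none |
| Week 37, Day 85 | 113 (41) | 141 (45) | none |
| Week 41, Day 113 | 141 (45) | 169 (49) | EOS only |

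The 3-day visit window changes no entry. In the last row, EOT would have to be 156 − 141 = 15 days late to count as Week 49. Read by cell position, Table 6-2 marks SPPB at Weeks 25, 33, 41 and 49 (EOT) and not at EOS. So 4 of 5 early-stop points give no Week 49 SPPB whatever the table reading, and 5 of 5 on the table as read. The table's alignment is damaged in the available text, so the fifth point is less certain.

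One exception to the 56 days: a patient stopped for a second missed dose may be identified after the 28-day point. For example, with Weeks 41 and 45 missed, the last dose is at Week 37. An EOT at about Day 141 still maps to Week 45.

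**3. Arm size.** About 45 patients (Protocol, Amendment 1 rationale) over 7 distinct regimens or 8 randomised cells: 45/7 = 6.4 and 45/8 = 5.6. An equal split is an assumption. Protocol Table 9-2 (40 to 50 per arm) does not describe this comparison.

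**4. Precision.** Half-width = t(0.975, n1 + n2 − 2) × SD × √(1/n1 + 1/n2). SD 2.0 is an assumption within the 1.5 to 3.0 range of Protocol 9.7.

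- 6 vs 6: 2.57. 5 vs 6: 2.74 (wider by 0.17).
- 5 vs 5: 2.92. 4 vs 5: 3.17 (wider by 0.25).

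At 6 vs 6 the half-width runs from 1.93 (SD 1.5) to 3.86 (SD 3.0).

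**5. Bias, under assumed inputs.** If stoppers' Week 49 mean would differ from completers' by the same gap in both arms:

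bias = (stop rate continued − stop rate switched) × (completer mean − stopper mean)

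- 10% vs 10%: 0 for any gap.
- 20% vs 10%: 0.10 × 0.5 = 0.05, up to 0.10 × 2.0 = 0.20.
- 30% vs 10%: 0.20 × 0.5 = 0.10, up to 0.20 × 2.0 = 0.40.

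The sign reverses if the switched arm loses more patients, or if stoppers would have scored higher. Protocol 6.3.2 takes a change of 1.0 as clinically relevant.

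**The case against.** A reader might infer that drug-related stops selectively empty the continued arms, leaving drug-tolerant patients to be compared with nearly all switched patients. The documents do not support that as a statement of fact. They give no stop rate by arm or cause, and the visit rule is the same, and blinded, in every arm. Prohibited medication, a broken blind, missed doses and a sponsor decision are not specific to active drug. All entrants had completed 24 weeks in the core study, and Protocol 3.6 expects drug effect to persist for some weeks in patients switched to placebo. SAP 3.2.1 will tabulate discontinuations and reasons by treatment group, so an imbalance would be visible afterwards. This objection stands: differential loss is a possibility, not a finding.

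A second inference, that early stoppers contribute nothing, is also wrong. SPPB values up to and including the early EOT enter the by-visit summaries, by-visit intervals and plots (SAP 3.5.2, 3.5.3.1).

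A third is that these patients' later scores would answer the amended durability question directly. They would not. That question concerns 24 weeks of treatment, whereas a continued-arm patient stopping after dose 1 to 4 has had extra doses and is 49 − 37 = 12 to 49 − 25 = 24 weeks past the last one at Week 49. Whether off-treatment values belong in the contrast is partly an estimand choice.

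Finally, the reach is small. No hypothesis is tested, and the intervals are wide with or without the loss. Applying the overall 30% dropout of Protocol Section 4 to the 10 to 15 ongoing patients (an assumption) gives about 3 to 5 people, some beyond reach through death or withdrawn consent. That limits the importance of the point but does not remove the mismatch.

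**Conclusion.** The point holds as a mismatch between the early-stop visit rule and the Week 49 endpoint. The timing follows from the documents alone: four of the five early-stop points have no visit in the Week 49 window, and the fifth has only an EOS at Day 169 with no SPPB marked in Table 6-2 as read.

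The consequence is modest. One lost patient widens a half-width that is already more than twice the relevant change by 0.17 to 0.25 points (SD 2.0, 5 or 6 per arm). Bias is unknown in size and direction: zero at equal stop rates, and about 0.05 to 0.40 points at assumed rates of 20% to 30% versus 10% with a gap of 0.5 to 2.0 points. The scope is about 45 patients, of whom 10 to 15 were expected to be ongoing at the amendment. It is worth correcting because the remedy is cheap and each value in these arms counts.

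**What to change.** Reconcile Protocol 5.5.10, Section 6 and Table 6-2 footnote 4 with the Week 49 endpoint by separating the end of infusions from the end of assessments:

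- keep the visit about 28 days after the last dose;
- have patients who have not withdrawn consent attend the remaining assessments already scheduled in Table 6-2, without infusion, with SPPB, 6MWT and DXA at calendar Week 49;
- state how the post-dose visit is labelled for analysis, so that it is not confused with the Week 49 EOT.

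The criteria for stopping treatment do not change.

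The cost is a written protocol amendment with the approvals required by Protocol 11.1, plus some visit burden for patients who have stopped drug. The assessments are ones Table 6-2 already contains. The change can help only patients whose Week 49 visit is still ahead.

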5.1 Protocol requested treatment

5.1.1 Investigational treatment

Patients newly enrolled after protocol amendment #1 will not receive any investigational treatment as part of this protocol.

For patients enrolled prior to protocol amendment #1 the investigational treatment is as follow:

- Bimagrumab [REDACTED] prepared by Novartis and supplied to the Investigator site as open labeled bulk medication.
- Placebo will be a Dextrose 5% in water infusion supplied by the site

Study drug preparation will be detailed in a separate pharmacy manual.

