5.5.9 Prohibited treatment

Any investigational treatment on a different protocol is forbidden at the time of enrollment or within 5 half-lives of the investigational treatment prior to enrollment.

Use of the treatments displayed in the table below are NOT allowed throughout the extension study). The following treatments are not allowed because of their biological effect on muscle anabolism or catabolism, which would potentially confound the assessment of efficacy.

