Patient can be discontinued if in the judgment of the investigator, taking into account the patient's overall status prevents the patient from safely continuing in the study.

Patients should then return to the site to perform the EOS visit as soon as possible and not later than 4 weeks after the decision being taken.

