
S : mark procedure documented in the patient's source file only and not in the CRF
 
* Assessment performed at EOT visit of the core study. 3rd party data will be automatically transferred.
 
¹ Site must re-enter the data from EOT of core study onto the corresponding eCRF page of the extension study
 
² Ongoing events/conditions (i.e. SAEs/AEs, concomitant medications, cardiovascular and other relevant medical history) at EOT of the core study must be recorded on the appropriate eCRF of the extension study
 
³ From the time of signing informed consent until EOS
 
⁴ From the time of signing informed consent until 30 days after a patient stopped study participation
 
⁵ Patients who discontinue study should return for EOS visit within the next 4 weeks unless they withdraw their consent
								

Table 6-2 Assessment schedule for patients enrolled prior to the protocol amendment #1

Epoch	Screening Epoch	Treatment Epoch												Post-treatment Follow-up Epoch
		1	2	3	4	5	6	7 (EOT) ⁴	8(EOS) ⁴					
Visit	1	1	2	3	4	5	6	7 (EOT) ⁴	8(EOS) ⁴					
Month	7	7	8	9	10	11	12	13	14					
Week	25	25	29	33	37	41	45	49	53					
Day	1	1	29	57	85	113	141	169	197					
Hours	Pre-dose	Pre-dose/ *EOT of core	0	Pre-dose	0	Pre-dose	0	Pre-dose	0	Pre-dose	0	Pre-dose	0	
Obtain informed consent	x													
Inclusion / Exclusion criteria	x													
Relevant med. hist. / Current med. cond./Cardiovascular medical his.		X ⁷												
Concomitant Meds / Therapies		X ⁷	Any time as per concomitant therapies reporting requirement											
Demography	X ⁸													
Physical examination ⁹		*8		s				s				s		s
Body weight		*8		x				x				x		x
Body height		*8												x
Blood pressure / Pulse rate (sitting)		*8		x				x				x		x ⁴
Electrocardiogram (ECG)		*8		x				x				x		x

Epoch	Screening Epoch	Treatment Epoch												Post-treatment Follow-up Epoch
		1	2	3	4	5	6	7 (EOT) ⁴	8(EOS) ⁴					
Visit	1	1	2	3	4	5	6	7 (EOT) ⁴	8(EOS) ⁴					
Month	7	7	8	9	10	11	12	13	14					
Week	25	25	29	33	37	41	45	49	53					
Day	1	1	29	57	85	113	141	169	197					
Hours	Pre-dose	Pre-dose/ *EOT of core	0	Pre-dose	0	Pre-dose	0	Pre-dose	0	Pre-dose	0	Pre-dose	0	
Echocardiography		*												x ¹⁰
Hematology		*		x				x						x
Clinical Chemistry		*		x				x						x
Cardiac Panel		*												
Vitamin D quantification		*						x						x
Vitamin D3 supplementation			Equivalent to daily administration of 800 IU to 4000 IU											
Supervised exercise		*8				x				x				x ⁴

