9.1 Analysis sets

Full analysis set (FAS): The FAS comprises all subjects enrolled in the study..

Safety set (SAF): The safety set comprises all subjects who received at least one dose of study drug from the core or extension study and enrolled in the extension study.

Per-protocol set (PP): The Per-protocol set comprises all subjects in the FAS who do not have major protocol deviations that could confound the interpretation of analyses conducted on the FAS. The following are common examples of such protocol deviations:

- Subject entered the study even though they did not satisfy the entry criteria
- Subject developed study/treatment withdrawal criteria during the study but was not withdrawn
- Subject received the wrong treatment or incorrect dose
- Subject took a prohibited concomitant medication

The PP set will be identified and finalized based on blinded review of the data, prior to the database lock.

To facilitate different analysis on patients enrolled before and after the protocol amendment, two populations are defined as in below:

- Population I is defined to include patients enrolled prior to protocol amendment 1, who will be continuing the treatment as originally assigned and follow the original schedule until end of the study.
- Population II is defined to include patients enrolled after protocol amendment 1, who will be followed up per schedule defined in this protocol amendment.

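### Population II patients who take a prohibited medicine must leave a follow-up with no study drug, so most such exits leave no Week 49 value

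*Protocol*

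**What the plan says.** Protocol 5.1.1 states: "Patients newly enrolled after protocol amendment #1 will not receive any investigational treatment as part of this protocol". For the same patients, Protocol 5.5.10 states: "Patients have to be discontinued from the study if they receive any of the prohibited medication listed in Section 5.5.9". Protocol 5.5.9 explains the prohibition by the medicines' effect on muscle, "which would potentially confound the assessment of efficacy". It gives no safety reason. A separate sentence in 5.5.10 lets the investigator discontinue a patient who cannot safely continue.

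After the decision, the patient is to "perform the EOS visit as soon as possible and not later than 4 weeks after the decision being taken". Table 6-1, footnote 5, repeats this: "Patients who discontinue study should return for EOS visit within the next 4 weeks unless they withdraw their consent". Section 6 adds that patients who discontinue the study are not to be regarded as withdrawn unless they withdraw consent, but asks only for the EOS visit and for contact covering "reporting and follow-up of serious adverse events during the 30 days following the last study visit". Under the Table 6-1 footnotes, adverse events are collected until EOS.

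The primary endpoint is SPPB at Week 49 (Protocol 9.4.1). It is analysed on the FAS, which is everyone enrolled, using observed data only (Protocol 9.1, 9.4.2, 9.4.3; SAP 3.4.3). The PP exclusions in Protocol 9.1 and SAP 3.1 already name this deviation: "Subject took a prohibited concomitant medication". The primary analysis is repeated on the PP set (Protocol 9.4.4).

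**The concern.** In Population II there is no investigational treatment to stop, so the main effect of the exit rule is to end observation. Its stated purpose, keeping confounded values out of the efficacy assessment, is an analysis matter, and the PP set already deals with it. Ending observation removes the Week 49 value from the FAS as well. On this deviation the FAS and PP results then tend to agree because the data were never collected, not because the medicine made no difference.

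A patient who starts a medicine acting on muscle may well do so after a change in health. If so, the missing values are not a random sample. They bear on the Population II summaries by core treatment and on the between-arm ANCOVA intervals in SAP 3.5.3.1 and 5.8.2. Long-term safety after withdrawal is a secondary objective (Protocol 2.2), and non-serious adverse events and laboratory values after the early EOS are not collected. Discontinued patients are not replaced (Protocol 5.5.12).

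**Working it through.** **When the Week 49 value is lost.** Inputs: EOS at most 28 days after the decision (Protocol 5.5.10; Table 6-1, footnote 5). SAP 5.5.1 assigns assessments by study day, with Week 49 covering days 156 to 183 and a target of day 169.

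- 156 - 28 = 128.
- Decision on days 1 to 127: the latest possible EOS is day 127 + 28 = 155, so no Week 49 value is possible.
- Decision on days 128 to 155: a Week 49 value is possible but not assured.
- Decision from day 156: the EOS visit falls in the window, provided it is held by day 183.
- Share of the 169-day follow-up with certain loss: 127/169 = 75%.

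DXA is scheduled only at Week 25 and EOS in Table 6-1, so lean mass has no other late measurement.

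**The plan's own figures.**

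- Protocol section 4 expects about 200 patients, 30% drop-out and about 140 completers: 200 x (1 - 0.30) = 140. This reproduces.
- Table 9-2 follows from 1.96 x SD / sqrt(n). At SD = 2.0 this gives 0.554 for n = 50 and 0.620 for n = 40, against the stated 0.55 and 0.62. All eight cells reproduce.

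**Number of values at risk.** The documents give no rate of prohibited-medicine use, so 5-10% is an assumption.

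- Population II: about 200 - 45 = 155, taking the 45 from the amendment rationale.
- Patients affected: 0.05 x 155 = 7.75 and 0.10 x 155 = 15.5, or about 8 to 16.
- Certainly lost if exits are spread evenly over days 1 to 169: 0.75 x 7.75 = 5.8 and 0.75 x 15.5 = 11.6, or about 6 to 12.

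**Precision cost at SD = 2.0, with the Table 9-2 formula.**

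| Planned n per arm | No loss | 5% lost | 10% lost |
|---|---|---|---|
| 40 | 0.620 | 0.636 | 0.653 |
| 50 | 0.554 | 0.569 | 0.584 |

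The widening is about 0.01 to 0.03 SPPB points. A more generous scenario takes 140 completers in four equal arms (assumed), 35 per arm, with a half-width of 0.66. If 10% to 50% of all drop-outs were these exits and were retained instead, the arms would hold 36.5 to 42.5 patients and the half-width would be 0.65 to 0.60. The gain is then about 0.01 to 0.06. Precision is therefore not the main issue; selective missingness is.

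**The case against.** The strongest counter-argument concerns the question being asked. Protocol 3.2 describes function maintained with no support beyond exercise and possibly vitamin D. A value taken after a muscle-active medicine does not answer that directly, and the sensitivity analysis proposed below would drop it. The study tests no hypothesis, and the primary Population II analysis is descriptive. That makes the rule a defensible choice rather than an error. It does not remove the point: a collected value can be excluded later, while an uncollected one cannot be recovered.

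Several stronger readings are tempting, and the documents do not support them:

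- **That data are thrown away.** Everything before exit stays in the FAS and safety set. The early EOS visit includes SPPB, 6MWT, DXA, laboratory tests and ECG. Serious adverse events are followed for 30 days, and suspected related ones are reportable after that (Protocol 7.2).
- **That every user loses the Week 49 value.** Exits decided from day 128 can still yield one.
- **That the FAS becomes a PP set.** Only one of the four listed examples of PP deviations is mainly affected.
- **That the PP definition presumes these patients stay to Week 49.** Its examples serve both populations and include patients who met withdrawal criteria but were not withdrawn, so it may also be a safety net.
- **That exit ends nothing but data collection.** Protocol 5.1.2 counts vitamin D and the exercise programme as study treatments, and 3.6 expects bimagrumab's effect to last a few weeks into the extension.

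Early end of follow-up is not unique to Population II. Population I patients who stop treatment also go to an early end-of-treatment visit and then EOS 4 weeks later, but there a study drug is being stopped.

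**Conclusion.** The point holds for this one deviation. A mandatory exit, justified only by confounding, makes a Week 49 value impossible for any decision before day 128 and ends later adverse event and laboratory collection. The Section 6 statement that such patients are not withdrawn does not cure this, because it still leaves them only the EOS visit; that wording and 5.5.10 need to be reconciled.

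The size is uncertain. With assumed use of 5-10% in about 155 patients, up to 8-16 Week 49 values are at risk. About 6-12 are certainly lost if exits are evenly spread, and fewer if some of these patients would have dropped out anyway. The effect on interval width is small. A reader might infer that bias has been shown. It has not: informative missingness is plausible, but neither its direction nor its size can be estimated from the documents.

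The day-128 limit rests on the SAP's study-day windows. If an early EOS were counted as Week 49 by its label, there would be no gap, but mistimed values would enter the primary endpoint.

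**What to change.** Make this a data-collection change only. Reconcile Protocol 5.5.10 with Section 6 and Table 6-1, footnote 5, so that use of a prohibited medicine does not by itself end scheduled data collection in Population II. The Week 37 and Week 49 visits and the phone calls would continue unless the patient withdraws consent or the investigator uses the safety exit already in 5.5.10.

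Record the medicine and its start date on the concomitant medication page already in use. Keep these patients in the FAS and exclude them from the PP set as planned. Add to the SAP one sensitivity analysis on the FAS that drops values after the start date. The list of prohibited medicines and all care decisions stay as they are.

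The cost is protocol wording and one extra analysis, since the visits and calls are already scheduled. The downside is that a few FAS values will be affected by the medicine, which the PP and sensitivity analyses address.
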